3.11 Definition of Subjects Lost to Follow-up

Subjects who cannot be contacted on or before their last trial visit and who do not have a known reason for discontinuation (eg, withdrew consent or AE) will be classified as “lost to follow-up” as the reason for withdrawal.

Every effort will be made by the investigator, or trial personnel, to contact the subject before the subject is declared lost to follow-up (see [Section 3.8.3.5.2](#)).

3.12 Subject Compliance

Dispensing of IMP and reconciliation will be done monthly during the randomized treatment period. Subject compliance will be monitored by pill counts as drug is returned. In addition, tolvaptan metabolite DM-4103 concentrations will be determined and evaluated for consistency with reported dosing.

Any subject who, without the instruction of the investigator, discontinues investigational product for 30 consecutive days or misses > 30% of the doses intended for a period (whichever is greater) will be deemed non-compliant. Depending on the circumstances leading to non-compliance, the subject may be discontinued from IMP administration by the investigator and/or sponsor. A subject who proactively wishes to discontinue IMP administration, or has IMP discontinued by the investigator, will be encouraged to continue limited participation in the trial, as described in [Section 3.8.3.3](#).

3.13 Protocol Deviations

In the event of a significant deviation from the protocol due to an emergency, accident, or mistake (eg, violation of informed consent process, IMP dispensing or subject dosing

error, treatment assignment error, subject enrolled in violation of eligibility criteria or concomitant medication criteria), the investigator or designee will contact the medical monitor at the earliest possible time by telephone. The investigator and sponsor will come as quickly as possible to a joint decision regarding the subject's continuation in the trial. This decision will be documented by the investigator and the sponsor, and reviewed by the site monitor.

4 Restrictions

4.1 Prohibited or Restricted Medications

Medications or surgical therapies used for the purpose or potential for modifying the progression of PKD cyst growth or development will be prohibited. These include, but are not restricted to, somatostatin agonists, rapamune (sirolimus), anti-sense ribonucleic acid (RNA) therapies, tolvaptan, and other vasopressin antagonists eg, OPC-31260 (mozavaptan), Vaprisol (conivaptan), or agonists (eg, desmopressin) and cyst decompression surgery.

Continuous or short-term use of other medications, while not prohibited, may be restricted by the investigator because of their potential for interference with metabolism or efficacy endpoints. This includes the use of diuretics which may be used intermittently, but not within 7 days of a urine assessment. Diuretics are not generally recommended in ADPKD due to their tendency to increase AVP levels through relative dehydration or volume depletion; thus, chronic use of diuretics (eg, for hypertension) will be prohibited due to potential endpoint interference and is an exclusionary criterion for this trial. Subjects taking such agents must first sign an ICF and then agree to be switched to an alternate form of therapy in order to be eligible for the trial. Some drugs are known to alter creatinine concentrations so, while not prohibited, subjects should alert their trial doctor, and any other health-care providers, to take this into consideration when considering changes in their prescribed or over-the-counter medications. A brief list would include: cimetidine, NSAID medications like aspirin or ibuprofen, chemotherapy drugs, and cephalosporin.

Since tolvaptan is a weak cytochrome P450 (CYP) 3A4 substrate, potent CYP3A4 inhibitors should be avoided during the trial, with the exception of amiodarone, which was found to have no effect on tolvaptan. A partial list of other CYP3A4 inhibitors can be found in Table 4.1-1.

boceprevir	clarithromycin	clotrimazole (if used orally)	indinavir
itraconazole	ketoconazole (if used orally)	lopinavir	mibefradil
nefazadone	nelfinavir	posaconazole	ritonavir
saquinavir	telaprevir	telithromycin	voriconazole

4.2 Dietary Restrictions and Recommendations

Restriction of excess dietary sodium and cooked meat protein may prove beneficial to subjects with a history of, or predisposition for, hypertension or kidney disease in general and should be applied to all subjects diagnosed with advanced ADPKD, particularly if there is evidence for a propensity for rapid progression. In the absence of alternate regional practices, restrictions of dietary salt < 5g/day and dietary cooked meat protein < 1 g/kg/day and to limit caffeinated drinks/foods should also be given (no more than 2 coffee equivalents per day).

Additionally, fluid intake is generally encouraged in subjects with PKD. Given the potential for dehydration with tolvaptan treatment, all subjects should be instructed to ingest fluids in anticipation of, or at the first sign of thirst in order to avoid excessive thirst or dehydration. Upon consent, all subjects should receive the recommendation to ingestion of at least 2-3 liters of fluid (including in solid, semi-solid, and liquid foods) per day, unless otherwise directed by your study doctor. This recommendation should start during screening and continue through the end of the trial. Additionally, subjects should ingest 1 to 2 cups of water before bedtime regardless of perceived thirst and replenish fluids overnight with each episode of nocturia. Dehydration will be monitored by subject self-assessment of changes in body weight and reporting of symptoms. Acute changes of > 3% of body weight (increase or decrease) over any 7-day period should be noted. Subjects should be instructed to report acute changes in body weight to the trial physician for further evaluation and recommendations.

Subjects should be advised that the ingestion of pomelo, grapefruit, or Seville orange products would be expected to increase tolvaptan concentrations and these should be avoided. In the event of an unintentional ingestion of such products, the investigator may ask the subject to temporarily interrupt IMP. Subjects should be informed of regionally appropriate recommendations in the trial ICF.

5 Reporting of Adverse Events

The following describes the methods and timing for assessing, recording, and analyzing safety parameters, as well as the procedures for eliciting reports of and recording and reporting AEs and intercurrent illnesses and the type and duration of the follow-up of subjects after AEs.

ADPKD is a progressive disorder involving the kidney, liver and occasionally other organ systems. A number of AEs may be associated with this disorder and are endpoints in this trial, including urine concentration defects, hypertension, renal pain, renal infection, nephrolithiasis, hematuria, and ESRD. As such, these events are considered “expected” in this trial population and will not qualify for the purposes of regulatory expedited reporting (eg, Suspected Unexpected Serious Adverse Reaction [SUSAR] and investigational new drug [IND] safety reports).

These blinded events will be evaluated on a regular basis by the trial’s Medical Monitor and the sponsor’s Safety group. The trial’s IDMC will include a separate statistical support group who will be provided the randomization codes so that partially or fully unblinded review of data may occur in closed session to better assess risk/benefit in the trial population.

5.1 Definitions

An AE is defined as any untoward medical occurrence associated with the use of a drug in humans, whether or not considered drug related.

A suspected adverse reaction means any AE for which there is a reasonable possibility that the drug caused the AE. For the purpose of IND safety reporting, “reasonable possibility” means there is evidence to suggest a causal relationship between the drug and the AE. Suspected adverse reaction implies a lesser degree of certainty about causality.

A SAE includes any event that results in any of the following outcomes:

1. death
2. life-threatening, ie, the subject was, in the opinion of the investigator, at immediate risk of death from the event as it occurred. It does not include an event that, had it occurred in a more severe form, might have caused death.
3. persistent or significant incapacity or substantial disruption of the ability to conduct normal life functions.
4. requires in-patient hospitalization or prolongs hospitalization
NOTE: A pre-scheduled hospitalization is not considered an SAE.
5. congenital anomaly/birth defect

6. other medically significant events that, based upon appropriate medical judgment, may jeopardize the subject and may require medical or surgical intervention to prevent one of the outcomes listed above, eg, allergic bronchospasm requiring intensive treatment in an emergency room or home, blood dyscrasias or convulsions that do not result in hospitalization, or the development of drug dependency or drug abuse.

Non-serious AEs are all AEs that do not meet the criteria for a “serious” AE.

Immediately Reportable Event (IRE):

- Any SAE
- Any AE (whether serious or non-serious) that necessitates discontinuation of IMP.
- Any subject with a new liver test abnormality meeting the AE (whether serious or non-serious) or laboratory threshold criteria (whether considered an AE or not) for hepatic eCRF reporting.
- Any subject reporting an AE of special interest (eg, skin neoplasms or glaucoma).
- Pregnancies are also defined as IREs. Although normal pregnancy is not an AE, it will mandate IMP discontinuation and must be reported on an IRE form to Otsuka Pharmaceutical Development & Commercialization, Inc. (OPDC). Pregnancy will only be documented on the AE eCRF if there is an abnormality or complication.
- Additionally, in the EU region, events involving overdose, misuse and abuse as well as reported lack of efficacy must also be reported as IREs.

Clinical Laboratory Changes: It is the investigator’s responsibility to review the results of all laboratory tests as they become available. This review will be documented by the investigator’s dated signature on the laboratory report. For each abnormal laboratory test result, the investigator needs to ascertain if this is an abnormal (ie, clinically significant) change from baseline for that individual subject. (This determination, however, does not necessarily need to be made the first time an abnormal value is observed. The investigator may repeat the laboratory test or request additional tests to verify the results of the original laboratory tests). If this laboratory value is determined by the investigator to be an abnormal change from baseline for that subject, this is considered an AE.

Severity: Adverse events will be graded on a 3-point scale and reported as indicated on the eCRF. The intensity of an adverse experience is defined as follows:

- 1 = Mild: Discomfort noticed, but no disruption to daily activity.
- 2 = Moderate: Discomfort sufficient to reduce or affect normal daily activity.
- 3 = Severe: Inability to work or perform normal daily activity.

IMP Causality: Assessment of causal relationship of an AE to the use of the IMP

- Related:** There is a reasonable possibility of a causal relationship.
- Possibly related:** There is a reasonable causal relationship between the IMP and the AE. Dechallenge is lacking or unclear.
- Unlikely related:** There is a temporal relationship to IMP administration, but there is not a reasonable causal relationship between the IMP and the AE.
- Not Related:** There is no temporal or reasonable relationship to the IMP administration.

5.2 Eliciting and Reporting Adverse Events

The investigator will periodically assess subjects for the occurrence of AEs. In order to avoid bias in eliciting AEs, subjects should be asked the following non-leading question: “How have you felt since your last visit?” All AEs (serious and non-serious) reported by the subject must be recorded on the source documents and eCRFs provided by the sponsor.

In addition, the sponsor must be notified immediately by telephone or fax of any immediately reportable events according to the procedure outlined below in [Section 5.3](#). Special attention should be paid to recording hospitalization and concomitant medications.

5.3 Immediately Reportable Events

The investigator must immediately report within 24 hours after either the investigator or site personnel become aware of any SAE, new liver lab abnormality requiring special liver eCRF completion, or confirmed pregnancy, by telephone or by fax to Quintiles drug safety services as outlined in Appendix 1. An IRE form must be completed and sent by fax or overnight courier to the sponsor. (Please note that the IRE form is NOT the AE eCRF.)

Non-serious events that require discontinuation of IMP (including laboratory abnormalities) should be reported to the sponsor within 3 working days. The IRE form must be completed and sent by fax or overnight courier to the sponsor.

Subjects experiencing SAEs should be followed clinically until their health has returned to baseline status, or until all parameters have returned to normal, or have otherwise been explained. It is expected that the investigator will provide or arrange appropriate supportive care for the subject.

For subjects discontinued from IMP, vital status and scheduled laboratory data will continue to be collected at scheduled monthly visits and at trial termination.

5.4 Pregnancy

Women of childbearing potential who are sexually active must use an effective method of birth control during the course of the trial and for 30 days after the last dose of IMP in a manner such that risk of failure is minimized. Unless the subject is sterile (ie, women who have had a bilateral oophorectomy and/or hysterectomy or have been postmenopausal for at least 12 consecutive months) or remains abstinent, 2 of the following precautions must be used: vasectomy, tubal ligation, intrauterine device, birth control pills, birth control depot injection, birth control implant, condom or occlusive cap (diaphragm or cervical/vault caps) with spermicide. Any single method of birth control, including vasectomy and tubal ligation, may fail, leading to pregnancy.

Before enrolling WOCBP in this clinical trial, investigators must review guidelines about trial participation for WOCBP. The topics should generally include:

- General information.
- ICF.
- Pregnancy prevention information.
- Drug interactions with hormonal contraceptives.
- Contraceptives in current use.
- Guidelines for the follow-up of a reported pregnancy.

Prior to trial enrollment, WOCBP must be advised of the importance of avoiding pregnancy during trial participation and the potential risk factors for an unintentional pregnancy. The subject must sign an informed consent form stating that the above-mentioned risk factors and the consequences were discussed with her.

During the trial, all WOCBP should be instructed to contact the investigator immediately if they suspect they might be pregnant (eg, missed or late menstrual cycle).

If a subject or investigator suspects that the subject may be pregnant prior to administration of the investigational product, administration must be withheld until the results of blood serum pregnancy tests are available. If the pregnancy is confirmed, the subject must not receive IMP or be enrolled in the trial. If pregnancy is suspected while the subject is receiving treatment, IMP must be withheld immediately (if reasonable, taking into consideration any potential withdrawal risks) until the result of a serum pregnancy test is known. If pregnancy is confirmed, IMP will be interrupted or withheld in an appropriate manner (eg, dose tapering if necessary for subject safety) and the

subject will continue to be monitored for the duration of the remainder of the trial or of their pregnancy. Subjects who permanently discontinue IMP due to pregnancy may continue to be monitored in the same manner as other subjects to their 12-month visit and will be considered trial Off-treatment completers.

The investigator must immediately notify the sponsor of any pregnancy associated with IMP exposure during the trial and for 30 days after the last dose of IMP and record the event on the IRE form and forward it to the sponsor. The sponsor will forward Pregnancy Surveillance Form(s) for monitoring the outcome of the pregnancy.

Protocol required procedures for IMP discontinuation and follow-up must be performed on the subject unless contraindicated by pregnancy (eg, x-ray studies). Other appropriate pregnancy follow-up procedures should be considered if indicated. In addition, the investigator must report to the sponsor, on appropriate Pregnancy Surveillance form(s), follow-up information regarding the course of the pregnancy, including perinatal and neonatal outcome. Infants will be followed for a minimum of 6 months.

5.5 Procedure for Breaking the Blind

The investigator is encouraged to contact the sponsor/Clinical Research Organization (CRO) medical advisor to discuss their rationale for unblinding. However, to prevent delays to the investigator or medical personnel responding to a potentially emergent situation, unblinding of IMP will not be dependent upon the investigator receiving approval from the sponsor/CRO medical advisor (ie, the investigator will be able to obtain the code break information independent of the sponsor/CRO medical advisor). The investigator must contact the sponsor/CRO medical advisor by telephone with an explanation of the need for opening the treatment assignment code within 24 hours of opening the code. If the blind is broken, the sponsor's Clinical Safety and Pharmacovigilance department (contact information provided in Appendix 1) will be notified immediately. Documentation of breaking the blind should be recorded in the subject's medical record with the date and time the blind was broken and the names of the personnel involved. Once the blind is broken for a given subject, that subject may not reinitiate treatment with IMP.

5.6 Follow-up of Adverse Events

For this trial, AEs will be followed up for 7 days in subjects who discontinued prior to randomization and for 21 days after the last dose of IMP has been administered (follow-up period) in subjects who were randomized.

Subjects experiencing SAEs should be followed clinically until their health has returned to baseline status, or until all parameters have returned to normal, or have otherwise been explained.

For subjects who have discontinued IMP but have not withdrawn from the trial, vital status, AEs, concomitant medications, ESRD status, and scheduled laboratory data (including serum creatinine data) are planned to be collected regardless of IMP discontinuation until the scheduled end of the trial.

5.6.1 Follow-up of Non-serious Adverse Events

Non-serious AEs that are identified on the last scheduled contact must be recorded on the AE eCRF with the current status noted. All non-serious events that are ongoing at this time will be recorded as ongoing on the eCRF.

5.6.2 Follow-up of Post-Trial Serious Adverse Events

Serious AEs that are identified on the last scheduled contact must be recorded on the AE eCRF page and reported to the sponsor according to the reporting procedures outlined in [Section 5.3](#). This may include unresolved previously reported SAEs, or new SAEs. The investigator will follow SAEs until the events are resolved, or the subject is lost to follow-up. Resolution means the subject has returned to the baseline state of health, or the investigator does not expect any further improvement or worsening of the subject's condition. The investigator will continue to report any significant follow-up information to OPDC up to the point the event has been resolved.

5.6.3 Follow-up and Reporting of Serious Adverse Events Occurring after Last Scheduled Contact

Any new SAEs reported by the subject to the investigator that occur after the last scheduled contact, and are determined by the investigator to be reasonably associated with the use of the IMP, should be reported to OPDC. This may include SAEs that are captured on follow-up telephone contact or at any other time point after the defined trial period (ie, up to last scheduled contact). The investigator should follow potentially IMP-related SAEs identified after the last scheduled contact until the events are resolved, or the subject is lost to follow-up. The investigator should continue to report any significant follow-up information to OPDC up to the point the event has been resolved.

6 Pharmacokinetic and Pharmacodynamic Analysis

6.1 Pharmacokinetic

Tolvaptan (OPC-41061) plasma concentrations may be used for a population PK analysis (that would be reported separately).

The DM-4103 metabolite has a half-life of approximately 180 hours and, consequently, is a good marker of long term compliance with dosing. DM-4103 concentrations will be reviewed for consistency with IMP dispensing and return records in order to determine compliance. Concentrations will be plotted by gender (male, female, total population) and modal dose within the previous treatment period and treatment day.

6.2 Pharmacodynamic

Urine osmolality and specific gravity will be summarized by treatment (tolvaptan or placebo) and time point using descriptive statistics. Baseline values will be from the sample obtained at the end of the placebo run-in period.

7 Statistical Analysis

7.1 Sample Size

7.1.1 Sample Size Estimation

In this sample size estimation, it is assumed that 3 calculations of eGFR will be obtained at baseline during a 3-week interval during screening (1-2 weeks) and placebo run-in (1 week), and another 3 calculations will be obtained post-treatment during a 2-week interval that begins 1 week after the end of treatment (3-week post-treatment follow-up). The mean of the 3 eGFR values observed during the screening and placebo-run periods will be set as the baseline and the mean of the 3 eGFR values observed during the post-treatment follow-up period will be set as the renal function measurement post-treatment. The timing of the baseline and post-treatment observations will be set to the median of the observation times in the 2-week interval, respectively. Thus, the pre-treatment baseline will be set at approximately 6 weeks prior to randomization, and the post-treatment renal function measurement will be set at approximately 2 weeks after the end of treatment.

Based on a Mixed Model Repeated Measurements (MMRM) analysis of the non-Japan CKD-3 subjects from Trial [REDACTED], the treatment difference in renal function at Month 12, based on the post-randomization baseline, is [REDACTED]. [REDACTED]

[REDACTED]
[REDACTED]
[REDACTED]
[REDACTED], we may assume the treatment difference in renal function is $1.07 \text{ mL/min/1.73 m}^2$ in our sample size calculation.

To investigate the reduction in intra-subject variation achieved by taking the mean of an increased number of observations at baseline and post-treatment follow-up, and its impact on the sample size, we have to estimate the intra-subject error and inter-subject error.

One of the approaches in sample size calculation for this protocol is to use MMRM to estimate the intra- and inter-subject variances. In the ADPKD phase 3 trial [REDACTED], there was a pre-treatment baseline visit and two post-treatment follow-up visits, along with other on-treatment visits. Assume these data follow the following model (denoted as $j = 0$ for baseline and $j = 37$ for follow-up, as well as $j = 4, 8, 12, \dots, 36$):

$$Y_{i,0} = \alpha_i + \varepsilon_{i,0} \quad (1)$$

$$Y_{i,j} = \alpha_i + \delta_{i,j} + \varepsilon_{i,j} \quad (2)$$

where $\delta_{i,j}$, as a random effect of change from pre-treatment baseline at visit j for subject i . These $\delta_{i,j}$ s jointly follow a multivariate normal distribution with means being $\delta_{p,j}$ for placebo subjects and $\delta_{T,j}$ for tolvaptan subjects. Their individual variance is assumed to be $\sigma_{\delta_j}^2$. These $\delta_{i,j}$ s are supposed to be correlated; however, their correlations are not utilized for the purpose of sample size calculation in this protocol. In addition, α_i s are assumed iid to have a normal distribution, $\varepsilon_{i,j}$ are assumed iid $N(0, \sigma^2)$, and these random variables are mutually independent. Then, the change from baseline data follows this common MMRM model

$$Y_{i,j} - Y_{i,0} = \delta_{i,j} - \varepsilon_{i,0} + \varepsilon_{i,j} = \zeta_{i,j} + \varepsilon_{i,j} \quad (3)$$

where $\zeta_{i,j} = \delta_{i,j} - \varepsilon_{i,0}$. Note that the variance of $\zeta_{i,j}$ (denoted by $\sigma_{\zeta_j}^2$) is equal to $\sigma_{\delta_j}^2 + \sigma^2$. This model becomes a one-way random effect model if we only consider the post-treatment follow-up visits for a treatment group. Thus, applying a one-way random effect model to the change from pre-treatment baseline to post-treatment follow-up data of placebo and tolvaptan respectively, in subjects who had both follow-up visits and baseline in [REDACTED], σ^2 is estimated as [REDACTED]. Take the average of these two estimates of σ^2 to obtain an estimate of σ^2 as 7.1 to be used in this sample size calculation, which is the σ^2 [REDACTED]. Note that

$$\text{Var}(Y_{i,j} - Y_{i,0}) = \sigma_{\delta_j}^2 + 2\sigma^2 \quad (4)$$

At Month 12, the SD (Standard Deviation) could be assumed as [REDACTED]. Then based on (4), $\sigma_{\delta,j}^2$ at Month 12 is estimated as 28.05 [REDACTED].

With k repeated measurements at pre-treatment baseline and at 12 month post-treatment follow-up in this trial, the baseline intra-subject variance and the follow-up intra-subject variance are reduced from σ^2 to σ^2/k respectively. Thus, the variance of average change from average baseline at Month 12 is $(\sigma_{\delta,12}^2 + \sigma^2/k) + \sigma^2/k$, which is estimated as 31.6 [REDACTED] when k = 4 and 32.8 [REDACTED] when k = 3. Here we have the following table of sample size:

# of Blood draws	1	2	3	4
90% power	1722	1434	1336	1288
85% power	1477	1230	1146	1106
80% power	1286	1070	998	962

From the sample size table, the increase of repeated measurement at baseline and follow-up reduces the sample size significantly initially but quickly loses its effect when k is greater than 3. It seems that 3 repeated measurements may be appropriate in order to avoid subjects' burden. Thus, with an assumption of 10% dropout rate in the trial, the total sample size (randomized subjects) would be approximately 1300.

In order to avoid excessive blood draws, mechanisms were undertaken to minimize the intra-subject variability by standardizing, as much as possible, the timing and conditions by which serum creatinine was assessed (in particular recommending a similar diet, avoiding variation in protein, especially cooked meat protein, intake and exercise pattern during these periods). In addition to the efforts to reduce variability by standardizing subject diet at the time of blood draws, the number of scheduled blood draws will help establish precision in the estimated measurements.

For the sample size of the key secondary endpoint, longitudinal analysis specified [REDACTED] was applied to the eGFR data of CKD-3 [REDACTED] subjects using post-randomization baseline, to obtain the estimates of the variance of inter-subject eGFR slope [REDACTED] and the variance of intra-subject eGFR observations [REDACTED]. The power calculation using the sample size formula provided by Lefante²¹ assumes the following:

- 1) placebo subjects would have an eGFR decline of 4.5 mL/min/ 1.73 m² per year;

- 2) tolvaptan subjects would have an eGFR decline reduced 25% compared with placebo subjects;
- 3) treatment duration is 1 year with monthly observations in eGFR.

In addition, the 1:1 randomization and the alpha (0.05, 2-sided) specified above in the sample size of the primary endpoint are also assumed in the sample size calculation. It is then estimated that 734 subjects are required for 90% power. Thus, with a total sample size of approximately 1300, the key secondary endpoint will have more than 90% power in detecting a slope difference in this trial.

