
Criteria for Evaluation:
	
Primary Efficacy Endpoint: Treatment difference in the change of eGFR from pre-treatment baseline to post-treatment follow-up, annualized (divided) by each subject's IMP treatment duration.
 
Secondary Endpoints: Key Secondary Efficacy Endpoint: Treatment difference in annualized slope of eGFR calculated for individual subjects using an appropriate baseline and available post-randomization, on-treatment assessments.
 
Safety Endpoints:
 
1) AEs2) Vital signs3) Clinical laboratory tests, including serum transaminases, total bilirubin (BT), alkaline phosphatase (ALP), and serum sodium. 
PK Endpoints: Plasma tolvaptan and metabolite(s), including DM-4103 plasma concentrations.
 
PD Endpoints: Uosm and urine specific gravity.
 
Exploratory Endpoints: [REDACTED]

---------------------------------	---

Statistical Methods:

Sample size: Based on a Mixed Model Repeated Measurements analysis of the [REDACTED] CKD-3 subjects from trial [REDACTED], the treatment difference in renal function at Month 12 is 1.07 in our sample size calculation. It is expected that the intra-subject variance is 14.2 and inter-subject variance is 28.05 at Month 12. With 3 repeated measures at pre-treatment baseline and post-treatment follow-up, respectively, the power calculation estimates that, for a 2-sided alpha set at 0.05 for a power of 90%, and with an assumption of 10% dropout rate in the trial, a total sample size of approximately 1300 subjects is needed.

Key Datasets for analysis: The following datasets are defined for this trial:

- [REDACTED]
- [REDACTED]
- [REDACTED]
- [REDACTED]

Primary efficacy analysis: [REDACTED]

Statistical Methods, cont.:
	
Key secondary efficacy analysis: [REDACTED]
 
Safety analyses: [REDACTED]

Trial Duration:
	
The duration of the double-blind, randomized treatment period will be 12 months. The total duration for each subject entered into the trial is approximately 15-17 months (including the pre-randomization and follow-up periods, and an additional 8 weeks for extension of the screening period in subjects for whom this is necessary).

Table of Contents

Protocol Synopsis	3
Table of Contents	11
List of In-text Tables	16
List of In-text Figures	17
List of Appendices	18
List of Abbreviations and Definitions of Terms	19
1 Introduction	22
1.1 Nonclinical Data	23
1.2 Clinical Data	23

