## **10 Interim Analysis**

An optional interim analysis was planned but will not be conducted, because, given the rapid final enrollment, the sponsor, upon receiving recommendation from the trial's Steering Committee, deemed the analysis might only bring a few month's difference in trial conclusion. Thus, without the interim analysis, the alpha level of the final analysis will be 0.05.

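### The Synopsis pairs 90% power with about 1300 randomized, but the plan's own table needs 1336; on the plan's inputs 1300 gives about 89%

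*Protocol*

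**What the plan says.** Protocol Section 7.1.1 builds the calculation for the primary endpoint from a between-subject variance of the Month 12 change and a within-subject variance, the latter estimated "as 7.1 to be used in this sample size calculation". It then prints Table 7.1-1, which SAP Section 4.1 repeats. The table titles state a difference of 1.07, alpha 0.05 and 10% dropout. In the 90% power row the totals are 1722, 1434, 1336 and 1288 for one, two, three and four draws.

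Both documents then settle on three draws and, with the same 10% dropout, say that "the total sample size (randomized subjects) would be approximately 1300". No visible text explains the step from 1336 to 1300.

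The Synopsis (Statistical Methods, Sample size) summarizes this calculation. It says that "the treatment difference in renal function at Month 12 is 1.07 in our sample size calculation", specifies three repeated measures at each end, and gives a total of about 1300 as what is needed "for a 2-sided alpha set at 0.05 for a power of 90%, and with an assumption of 10% dropout rate in the trial". Protocol Sections 3.3 (Trial Population) and 7.4.5 (Interim Analysis) treat 1300 as the operative total.

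**The concern.** A sample size that delivers a target power is a minimum. If it is rounded down, the power attached to it should come down too. The Synopsis keeps the full 90% beside the smaller number, so it disagrees with the table it summarizes. A reader who sees only the Synopsis takes away a power that the stated size, dropout and variance do not produce. What is at stake is the accuracy of one planning figure for the primary test.

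**Working it through.** **Inputs**

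| Quantity | Value | Source |
|---|---|---|
| Difference | 1.07 mL/min/1.73 m² | Synopsis; Protocol 7.1.1; SAP 4.1 |
| Between-subject variance of change, Month 12 | 28.05 | Protocol 7.1.1; SAP 4.1 |
| Within-subject variance per measurement | 7.1 | Protocol 7.1.1 |
| Draws at each end, k | 3 | Protocol 7.1.1; SAP 4.1 |
| Alpha | 0.05, two-sided | Synopsis; SAP Section 10 |
| Allocation | 1:1 | Synopsis |
| Dropout | 10% | Synopsis; Protocol 7.1.1; SAP 4.1 |

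Two inputs need a remark. The Synopsis says "It is expected that the intra-subject variance is 14.2 and inter-subject variance is 28.05 at Month 12". Its 14.2 is 2 × 7.1, the sum of the baseline and follow-up contributions for single draws, so it agrees with Section 7.1.1. On alpha, Protocol 7.4.5 would have left 0.049002 for the final test after an interim analysis. SAP Section 10 drops the interim and says that "the alpha level of the final analysis will be 0.05".

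**Step 1: variance with three draws.** The plan's formula gives 28.05 + 7.1/3 + 7.1/3 = 32.78, SD 5.73. Protocol 7.1.1 prints 32.8, and the SAP's sample size re-calculation memorandum gives the SD as 5.73.

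**Step 2: reproduce the table.** For a two-sample comparison of means, normal approximation, inflated for dropout:

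N = 4 × (1.960 + 1.2816)² × variance / 1.07² / (1 − 0.10)

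- k = 1: variance 42.25, N = 1723 (table 1722)
- k = 2: variance 35.15, N = 1434 (table 1434)
- k = 3: variance 32.78, N = 1337 (table 1336)
- k = 4: variance 31.60, N = 1289 (table 1288)

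Rounding up within each arm at k = 3 gives 602 per arm, 1204 evaluable and 1204/0.9 = 1338 randomized. The table is therefore sound, and it already includes the dropout.

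**Step 3: power at 1300.** Evaluable subjects are 1300 × 0.9 = 1170, or 585 per arm.

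Power = Φ(1.07 / √(2 × 32.78 / 585) − 1.960) = Φ(3.196 − 1.960) = 89.2%

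The noncentral t distribution gives 89.1%. Alpha 0.049002 would give 89.0%.

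**Step 4: comparison.** At 1336 randomized (601.2 evaluable per arm) the same formula gives 90.0%. The shortfall is 1336 − 1300 = 36 subjects, 36/1336 = 2.7%, and 90.0 − 89.2 = 0.8 percentage points.

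**Step 5: losses at which 1300 would suffice.** 1 − 1204/1300 = 7.4%.

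**The case against.** The best defence is that the gap is within rounding. Both documents call the 1300 approximate, and the table with the exact 1336 stands directly above that sentence in each. Moreover, 89.2% counts every dropout as lost. The primary efficacy population keeps a subject who stops treatment early but has at least one valid post-treatment eGFR (Protocol 7.2), and SAP Section 8.1.1 widens the follow-up window to 7 to 40 days to limit exclusions. The primary ANCOVA also adjusts for baseline, which the formula ignores. Real power could therefore be at or above 90%.

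Much of this stands. A difference of 0.8 points is smaller than the precision of any planning model, and no decision turns on it. But the defence does not rescue the stated figure. The plan's calculation credits neither the retained discontinuers nor the baseline adjustment, and the Synopsis presents its 90% as the result of that calculation at 10% dropout. Retained early discontinuers also carry reduced weight in the weighted analysis, so they are not a one-for-one replacement. The word approximately qualifies the count, not the power.

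The location of the claim is also limited. Only the Synopsis joins 90% to 1300 for the primary endpoint. The sentence on 90% power later in Protocol 7.1.1 and SAP 4.1 concerns the key secondary endpoint, for which 734 subjects are said to be enough.

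**Conclusion.** The Synopsis figure is wrong as written, by a small amount. Under the plan's own variance, difference, alpha and 10% dropout, 1300 randomized gives about 89.2% power, and 90% needs 1336. This rests on the normal approximation and on treating dropouts as contributing nothing, as the plan's table does.

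Three stronger readings are tempting, and the documents support none of them:

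- **That the trial is underpowered.** A planned power of 89% is not materially different from 90%.
- **That the sample size calculation is faulty.** The 90% row reproduces to within one or two subjects.
- **That the missing 36 subjects matter to the blinded re-estimation.** The SAP's memorandum says an SD of 6.5 would still leave at least 80% power. At that SD, 1300 gives 80.4% and 1336 gives about 81.4%, so its statement holds either way. The open question in that memorandum is the size of the SD itself, which is a separate matter.

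**What to change.** In the Synopsis, restate the power for the primary endpoint as about 89% with 1300 randomized and 10% dropout, and note that 1336 would be needed for 90%. Optionally, put the same figure beside the 1300 in Protocol Section 7.1.1 and SAP Section 4.1. In those two places this adds a figure rather than correcting one.

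The cost is one sentence and a planning power that reads slightly less favourably. Enrolment, alpha, populations and analyses stay as they are.
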